7.2. Concomitant Medication

The term ‘concomitant medication’ refers to any medication that the patient receives at any time during the study, i.e. from screening to EOS visit. This includes the screening/baseline period,

treatment period and follow-up as defined in the protocol. At each visit, the Investigator will ask the patient about any medication taken since the last visit. All concomitant medication must be recorded in the patient’s medical file and documented on the appropriate pages of the eCRF.

Treatments not allowed during the study are the following:

- Plasma exchange, blood products or derivatives other than the study drug.

- Immunomodulators/immunosuppressors agents (e.g. including but not limited to cyclophosphamide, cyclosporine, interferon- α , interferon- β 1a, anti-CD20, alemtuzumab, aziathioprine, etanercept, mycophenolate mofetil, methotrexate) and haematopoietic stem cell transplantation.
- Introduction or increasing dose of systemic corticosteroids therapy, and/or systemic corticosteroids therapy at a dose higher than 10 mg prednisolone per day, or equivalent. Topical corticosteroids are permitted.
- Loop diuretics administered during the last 24 hours before IVIg infusion planned date. In this case, the study drug infusion date will have to be postponed.

Routine pre-medication (to prevent known drug related adverse reaction) are not recommended to avoid masking potential AEs. However, patients who have routinely been receiving pre-medication with previous Ig treatments may continue to receive the same pre-medication.

Other medications which are necessary for the patient's welfare or well-being may be given at the discretion of the Investigator.

All concomitant medications must be recorded in the patient's medical records and documented on the appropriate pages of the eCRF.

8. STUDY PLAN

The method for assessing each study parameter is described in Section [10](#).

See also [Table 1–1](#): study flow chart.

8.1. Patient recruitment

8.1.1. Informed Consent

The Investigator provides each patient with relevant, comprehensive, verbal and written information regarding the objectives and procedures of the study, as well as the possible risks involved. A patient information sheet will be given to the patient.

The patient should have enough time and opportunity to inquire about study details. All his/her questions should be answered in a satisfactory manner. The patient must be informed about his/her right to withdraw from the study at any time.

[figure not shown]
Signed informed consent must be obtained from the patient prior to undertaking any study-related procedure and before a blood sample is taken for the screening tests.

One original of the informed consent form, signed and dated by both the patient and the Investigator, will be given to the patient. A second original is filed at the Investigator's site. The process of obtaining consent will be documented in the patient's file.

8.1.2. Screening

The screening period starts when the patient signs his/her informed consent and ends right before study drug is first administered.

Figure 8–1: Sequence of study procedure

* ultrasonography coupled to electrophysiology (only for Italian sites).

8.2. Sequence of study procedures

8.2.1. Visit 1: Screening

The following visit procedures will be carried out during the screening:

- Informed consent signature.
- Check of inclusion and exclusion criteria.
- Demographic and biometric information (gender, age, weight, BMI...).
- Relevant medical history and ongoing concomitant diseases.
- Listing of prior medications.
- Complete physical examination.
- Vital signs: temperature, heart rate, systolic and diastolic blood pressure.

- Neurological status assessment:
 - INCAT disability score (adjusted INCAT disability score will be deduced from reported values).

- Biological tests in local laboratory:
 - Haematology:
 - Complete blood count + differentials, haemoglobin (Hb), mean corpuscular volume (MCV), platelets count.
 - Haptoglobin.
 - Reticulocytes, direct Coombs test.
 - Biochemistry:
 - Creatinemia, glomerular filtration rate according to MDRD.
 - LDH.
 - Total and free bilirubin (total bilirubin in all patients; if total bilirubin > ULN, free bilirubin will be assessed from the same blood sample, as total bilirubin).
 - AST, ALT, ALP, γ GT.
 - HbA1c (only for patients with a known history of diabetes mellitus).
 - Total serum protein level.
 - HBs Ag, anti HBs & anti HBc Ab, HIV, HCV tests.
 - Serum IgA levels.
 - Urine protein reagent strip test:

If urine protein reagent strip test result = Negative or Trace	Action: No further urine test required
If urine protein reagent strip test result = 1 cross (1 +)	Action: Verify eligibility after either assessing AER or PER from a 24h-urine collection sampled before the first study drug course or assessing ACR or PCR from a spot urine sample immediately following the urine protein reagent strip test (i.e. urine obtained before study drug administration).
If urine protein reagent strip test result = 2 crosses (2 +) or more	Patient should be excluded

- Urine Pregnancy test for female patients of child bearing potential.

- Analysis at centralised laboratory:
 - Anti-CNTN1 and anti-NF155 antibodies.
- Ultrasonography coupled to neurophysiology (for Italian sites only).
- AEs assessment.
- Listing of ongoing concomitant treatments.
- Delivery of Patient diary with instruction for use. The patient should document in the diary any AE that occurs outside of hospital (including start and end date and time) and any medication taken during the study. The patient should come back at each visit with the diary and the Investigator should assess and evaluate patient information recorded in the diary and report appropriate relevant information in the eCRF.

Abnormal findings at screening physical and biological tests should be reported as baseline findings in patient medical history. All clinical or laboratory abnormalities other than those found on mandatory study screening tests should be reported as an adverse event if clinically significant.

8.2.2. Visit 2: First study drug course

(As soon as the biologic results of screening are available, no later than 4 weeks after the start of the screening).

The following study procedures will be carried out at the 1st study drug course:

- Before the 1st study drug course (within 24 hours before study drug course)
 - Complete physical examination.
 - Biometric information: weight.
 - Vital signs: temperature, heart rate, systolic and diastolic blood pressure.
 - Baseline neurological status assessment:
 - INCAT disability score (adjusted INCAT disability score will be deduced from reported values).
 - Patient and Investigator CGI-S.
 - MRC-sum-score.
 - Rasch-modified MRC sum score.
 - R-ODS.
 - Grip strength with Martin vigorimeter in both hands.
 - Biological tests in local laboratory:
 - Serum total IgG trough levels.
 - C3 and C4 antigens.
 - Serum reference sample for long term storage.
 - Analysis at centralised laboratory:
 - BAFF.
 - CH50.
 - FcγRIIB.

- AEs assessment.
- Listing of concomitant medication.
- Patient diary verification. If information on the patient's diary is not clear, the Investigator will ask the patient questions. The investigator may annotate the patient's diary but must date and sign the annotations.
- During the course of study drug infusion:
 - Collection of infusion parameters.
 - Vital signs measured 30-45 min and 60-75 min after the beginning of the infusion: temperature, heart rate, systolic and diastolic blood pressure.
 - Listing of concomitant medication if applicable.
 - AEs assessment.
- 30-45 min after the end of study drug infusion:
 - Vital signs: temperature, heart rate, systolic and diastolic blood pressure.
 - AEs assessment.
 - Listing of concomitant medication if applicable.

8.2.3. Visit 3: 96 hours after the end of the first course (+/- 24 hours)

The following study procedures will be carried out:

- Complete physical examination.
- Vital signs: temperature, heart rate, systolic and diastolic blood pressure.
- Biological tests in local laboratory:
 - Haematology:
 - Complete blood count + differentials, Hb, MCV, platelets count.
 - Haptoglobin.
 - Biochemical:
 - Creatininemia, glomerular filtration rate according to MDRD.
 - LDH.
 - Total and free bilirubin (total and free bilirubin (total bilirubin in all patients; if total bilirubin > ULN, free bilirubin will be assessed from the same blood sample, as total bilirubin).
 - C3 and C4 antigens.
 - Urine protein reagent strip test [to be performed in patients who at screening tested for urine protein reagent strip result "1 cross 1 (+) and/or had GFR in the range of 60-80 mL/min/1.73m²]:

If urine protein reagent strip test result = Negative or Trace	Action: No further urine test required
If urine protein reagent strip test result = 1 cross (1 +) or more	Action: Assess either AER or PER from a 24h-urine collection sampled at least 7 days after the end of the previous study drug course or assess ACR or PCR from a spot urine sample immediately following the urine protein reagent strip test (i.e. urine obtained before study drug administration). The Investigator must review these results in time prior to the study drug administration and consider if any of the Early Discontinuation Criteria / Stopping Rules (see Section 5.4) apply.

- Analysis at centralised laboratory:
 - BAFF.
 - CH50.
 - FcγRIIB (on B cells).
- AEs assessment.
- Listing of concomitant medication if applicable.
- Patient diary verification. If information on the patient’s diary is not clear, the Investigator will ask the patient questions. The investigator may annotate the patient’s diary but must date and sign the annotations.

8.2.4. Visits 4, 5 and 6: Week 3, Week 6 and Week 9 (+/- 7 days)

The following study procedures will be carried out:

- Before study drug course (within 24 hours before study drug course)
 - Clinical examination focused on arterial or venous thromboembolic signs.
 - Biometric information: weight.
 - Vital signs: temperature, heart rate, systolic and diastolic blood pressure.
- Neurological assessments:
 - INCAT disability score (adjusted INCAT disability score will be deduced from reported values).
- Biological tests in local laboratory:
 - Haematology:
 - Complete blood count + differentials, Hb, MCV, platelets count.
 - Haptoglobin.
 - Biochemistry:
 - Creatininemia, glomerular filtration rate according to MDRD.
 - LDH.
 - Total and free bilirubin (total bilirubin in all patients; if total bilirubin > ULN, free bilirubin will be assessed from the same blood sample, as total bilirubin).
 - C3 and C4 antigens (only at visit V4, Week 3).
 - Serum total IgG trough levels.
 - Urine protein reagent strip test [to be performed before study drug administration in patients who at screening tested for urine protein reagent strip result "1 cross 1 (+) and/or had GFR in the range of 60-80 mL/min/1.73m²]:

If urine protein reagent strip test result = Negative or Trace	Action: No further urine test required
If urine protein reagent strip test result = 1 cross (1 +) or more	Action: Assess either AER or PER from a 24h-urine collection sampled at least 7 days after the end of the previous study drug course or assess ACR or PCR from a spot urine sample immediately following the urine protein reagent strip test (i.e. urine obtained before study drug administration). The Investigator must review these results in time prior to the next study drug administration and consider if any of the Early Discontinuation Criteria / Stopping Rules (see Section 5.4) apply.

- Blood collection for central analysis: (Week 3 only):
 - BAFF.
 - CH50.
 - FcγRIIB (on B cells).
- AEs assessment.
- Listing of ongoing concomitant treatments.
- Patient diary verification. If information on the patient’s diary is not clear, the Investigator will ask the patient questions. The investigator may annotate the patient’s diary but must date and sign the annotations.
- During the course of study drug infusion:
 - Collection of infusion parameters.
 - Vital signs measured 30-45 min and 60-75 min after the beginning of the infusion: temperature, heart rate, systolic and diastolic blood pressure.
 - Listing of concomitant medication if applicable.
 - AEs assessment.
- 30-45 min after the end of study drug infusion:
 - Vital signs: temperature, heart rate, systolic and diastolic blood pressure.
 - AEs assessment.
 - Listing of concomitant medication if applicable.

Four days after the end of study drug administration (+/- 1 day): the Investigator or the Study Nurse will call the patient in order to collect information about the possible occurrence of AEs after the patient has left the hospital.

8.2.5. Visit 7: Week 12 (+/- 7 days)

The following study procedures will be carried out:

- Before study drug course (within 24 hours before study drug course)
 - Clinical examination focused on arterial or venous thromboembolic signs.
 - Biometric information: weight.
 - Vital signs: temperature, heart rate, systolic and diastolic blood pressure.
 - Neurological status assessment:
 - INCAT disability score (adjusted INCAT disability score will be deduced from reported values).
 - Patient and Investigator CGI-S, CGI-E and CGI-I.
 - MRC sum score.

- Rasch-modified MRC sum score.
 - R-ODS.
 - Grip strength with Martin vigorimeter in both hands.
- Biological tests in local laboratory:
- Haematology:
 - Complete blood count + differentials, Hb, MCV, platelets count.
 - Haptoglobin.
 - Biochemistry:
 - Creatinemia, glomerular filtration rate according to MDRD
 - LDH.
 - Total and free bilirubin (total bilirubin in all patients; if total bilirubin > ULN, free bilirubin will be assessed from the same blood sample, as total bilirubin).
 - Serum total IgG trough levels.
 - Urine protein reagent strip test [to be performed before study drug administration in patients who at screening tested for urine protein reagent strip result "1 cross 1 (+) and/or had GFR in the range of 60-80 mL/min/1.73m²]:

If urine protein reagent strip test result = Negative or Trace	Action: No further urine test required
If urine protein reagent strip test result = 1 cross (1 +) or more	
Action: Assess either AER or PER from a 24h-urine collection sampled at least 7 days after the end of the previous study drug course
 
or assess ACR or PCR from a spot urine sample immediately following the urine protein reagent strip test (i.e. urine obtained before study drug administration).
 
The Investigator must review these results in time prior to the next study drug administration and consider if any of the Early Discontinuation Criteria / Stopping Rules (see Section 5.4) apply.

- AEs assessment.
 - Listing of ongoing concomitant treatments.
 - Patient diary verification. If information on the patient's diary is not clear, the Investigator will ask the patient questions. The investigator may annotate the patient's diary but must date and sign the annotations.
- During the course of study drug infusion:
 - Collection of infusion parameters.
 - Vital signs measured 30-45 min and 60-75 min after the beginning of the infusion: temperature, heart rate, systolic and diastolic blood pressure.
 - Listing of concomitant medication if applicable.
 - AEs assessment.
 - 30-45 min after the end of study drug infusion:
 - Vital signs: temperature, heart rate, systolic and diastolic blood pressure.
 - AEs assessment.
 - Listing of concomitant medication if applicable.

Four days after the end of study drug administration (+/- 1 day): the Investigator or the Study Nurse will call the patient in order to collect information about the possible occurrence of AEs after the patient has left the hospital.

8.2.6. Visits 8, 9 and 10: Week 15, 18 and 21 (+/- 7 days)

The following study procedures will be carried out:

- Before study drug course (within 24 hours before study drug course)
 - Clinical examination focused on arterial or venous thromboembolic signs.
 - Biometric information: weight.
 - Vital signs: temperature, heart rate, systolic and diastolic blood pressure.
- Neurological assessments:
 - INCAT disability score (adjusted INCAT disability score will be deduced from reported values).
- Biological tests in local laboratory:
 - Haematology:
 - Complete blood count + differentials, Hb, MCV, platelets count.
 - Haptoglobin.
 - Biochemistry:
 - Creatinemia, glomerular filtration rate according to MDRD.
 - LDH.
 - Total and free bilirubin (total bilirubin in all patients; if total bilirubin > ULN, free bilirubin will be assessed from the same blood sample, as total bilirubin).
 - Serum total IgG trough levels.
 - Urine protein reagent strip test [to be performed before study drug administration in patients who at screening tested for urine protein reagent strip result "1 cross 1 (+) and/or had GFR in the range of 60-80 mL/min/1.73m²]:

If urine protein reagent strip test result = Negative or Trace	Action: No further urine test required
If urine protein reagent strip test result = 1 cross (1 +) or more	
Action: Assess either AER or PER from a 24h-urine collection sampled at least 7 days after the end of the previous study drug course
 
or assess ACR or PCR from a spot urine sample immediately following the urine protein reagent strip test (i.e. urine obtained before study drug administration).
 
The Investigator must review these results in time prior to the next study drug administration and consider if any of the Early Discontinuation Criteria / Stopping Rules (see Section 5.4) apply.

- AEs assessment.
 - Listing of ongoing concomitant treatments.
 - Patient diary verification. If information on the patient’s diary is not clear, the Investigator will ask the patient questions. The investigator may annotate the patient’s diary but must date and sign the annotations.
- During the course of study drug infusion:
 - Collection of infusion parameters.
 - Vital signs measured 30-45 min and 60-75 min after the beginning of the infusion: temperature, heart rate, systolic and diastolic blood pressure.
 - Listing of concomitant medication if applicable.
 - AEs assessment.
 - 30-45 min after the end of study drug infusion:
 - Vital signs: temperature, heart rate, systolic and diastolic blood pressure.
 - AEs assessment.

Four days after the end of study drug administration (+/- 1 day): the Investigator or the Study Nurse will call the patient in order to collect information about the possible occurrence of AEs after the patient has left the hospital.

8.2.7. Visit 11: Week 24 (+/- 7 days) - End of study visit

At the end of the 24-week treatment and follow-up period, patients undergo an end of study visit evaluation. This visit occurs 3 weeks after the 7th course of study drug at a dose of 1 g/kg.

In the event of premature discontinuation from the study drug or patient withdrawal from the study, an end of study visit is performed within 7 days.

The end of study assessment should be performed before any other treatment including Igs is administered.

The reason for premature study drug discontinuation / study withdrawal should be accurately assessed and entered into the eCRF.

The following study procedures will be carried out:

- Complete physical examination.
- Biometric information: weight.
- Vital signs: temperature, heart rate, systolic and diastolic blood pressure.
- Neurological status assessment:
 - INCAT disability score (adjusted INCAT disability score will be deduced from reported values).
 - Patient and Investigator CGI-S, CGI-E and CGI-I.
 - MRC sum score.
 - Rasch-modified MRC sum score.
 - R-ODS.
 - Grip strength with Martin vigorimeter in both hands.
- Biological tests in local laboratory:
 - Haematology:

- Complete blood count + differentials, Hb, MCV, platelets count.
- Haptoglobin.
- Reticulocytes, direct Coombs test
- Biochemistry:
 - Creatininemia, glomerular filtration rate according to MDRD.
 - LDH.
 - Total and free bilirubin (total bilirubin in all patients; if total bilirubin > ULN, free bilirubin will be assessed from the same blood sample, as total bilirubin).
 - AST, ALT, ALP, γ GT.
 - Total serum protein level.
 - C3 and C4 antigens.
 - Serum total IgG trough levels.
- HBs Ag, anti HBs & anti HBc Ab, HIV, HCV tests.
- Serum reference sample for long term storage.
- Urine protein reagent strip test [to be performed before study drug administration in patients who at screening tested for urine protein reagent strip result "1 cross 1 (+) and/or had GFR in the range of 60-80 mL/min/1.73m²]:

If urine protein reagent strip test result = Negative or Trace	Action: No further urine test required
If urine protein reagent strip test result = 1 cross (1 +) or more	Action: Assess either AER or PER from a 24h-urine collection sampled at least 7 days after the end of the previous study drug course or assess ACR or PCR from a spot urine sample immediately following the urine protein reagent strip test (i.e. urine obtained before study drug administration).

- Urine Pregnancy test for female patients of child bearing potential.
- Analysis at centralised laboratory:
 - BAFF.
 - CH50.
 - Anti-CNTN1 and anti-NF155 antibodies.
- Ultrasonography coupled to neurophysiology (for Italian sites only).
- AEs assessment.
- Listing of concomitant treatments.
- Patient diary verification. If information on the patient's diary is not clear, the Investigator will ask the patient questions. The investigator may annotate the patient's diary but must date and sign the annotations.

8.3. At any course

In case of suspected clinical venous thrombosis: D-Dimers testing will be performed.

In case of suspected haemolysis based on biological tests (Hb, haptoglobin, LDH, total and free bilirubin levels (total bilirubin in all patients; if total bilirubin > ULN, free bilirubin will be assessed from the same blood sample, as total bilirubin)): Reticulocytes and direct Coombs test will be performed.

8.4. Central biological handling sampling

Details for blood sampling performed for the biomarkers (anti-CNTN1 and anti-NF155 antibodies, BAFF, CH50, FcγRIIB), storage and shipment to the central laboratory are described in the laboratory manual.

8.5. Ultrasonography (for Italian site only)

Details for ultrasonography coupled to neurophysiology examination are described in the ultrasonography manual.

8.6. Compliance with the study plan

The Investigator should make every effort to comply with the study plan. If the Investigator encounters difficulties in complying with the study plan, e.g. with regard to the schedule of visits or the required procedures, he/she must alert the Sponsor. The Sponsor may consider it relevant to generate an amendment.

The Investigator should make every effort to avoid the occurrence of deviations from the study plan. If deviations occur or if the Investigator knows that a deviation will occur, he/she must promptly inform the Sponsor to determine how to manage the deviation.

9. SAFETY

9.1. Reference Safety Information Document

The current version of the Investigator Brochure of I10E, will be the Reference Safety Information document to assess the expectedness of AEs.

9.2. Benefit / Risk Information

9.2.1. Potential risk(s) related to the study drug

Common and important adverse reactions associated with IVIg administration are described in the European Guideline EMA/CHMP/BPWP/94038/2007 rev.4 of IVIg [[14](#)].

Adverse reactions such as chills, headache, dizziness, fever, vomiting, allergic reactions, nausea, arthralgia, low blood pressure and moderate low back pain may occur occasionally with IVIg.

Rarely human normal Ig may cause a sudden fall in blood pressure and, in isolated cases, anaphylactic reaction, even when the patient has shown no hypersensitivity to previous administration.

Cases of reversible aseptic meningitis and rare cases of transient cutaneous reactions have been observed with human normal immunoglobulin. Reversible haemolytic reactions have been observed in patients, especially those with blood groups A, B, and AB. Rarely, haemolytic anaemia requiring transfusion may develop after high dose IVIg treatment.

Increase in serum creatinine level and/or acute renal failure have been observed.

Very rarely, thromboembolic reactions such as myocardial infarction, stroke, pulmonary embolism, deep vein thromboses have been described.

Important potential risks that could be anticipated with I10E administration are those known with IVIg preparations:

Hypersensitivity

True hypersensitivity reactions are rare. They can occur in patients with anti-IgA antibodies.

Rarely, human normal immunoglobulins can induce a fall in blood pressure with anaphylactic reaction, even in patients who had tolerated previous treatment with human normal immunoglobulins.

To minimize risk of anaphylactic reactions, patients with IgA deficiency will be excluded, except if the absence of anti-IgA antibodies is documented [37] [38]. The patients with a known hypersensitivity to the active substance or to any of the excipients of I10E will be excluded.

Thromboembolism

There is clinical evidence of an association between IVIg administration and thromboembolic events such as myocardial infarction, cerebral vascular accident (including stroke), pulmonary embolism and deep vein thromboses. Such an association is assumed to be related to a relative increase in blood viscosity through the high influx of immunoglobulins in at-risk patients.

To minimize the risk of thromboembolic events, patients with a history of venous thromboembolic disease, myocardial infarction or cerebrovascular accident will be excluded. As well, patients with uncontrolled cardiac arrhythmia and patients with unstable ischemic heart disease will not be allowed to participate to the study.

Acute renal failure

Cases of acute renal failure have been reported in patients receiving IVIg therapy. In most cases, risk factors have been identified. These included pre-existing renal insufficiency, diabetes mellitus, hypovolaemia, overweight, concomitant nephrotoxic medicinal products and age over 65.

To minimize the risk of acute renal failure, patients with a chronic kidney disease (CKD) defined as abnormalities of kidney structure or function, present for >3 months, with implications for health, i.e. patients with persistent albuminuria category A3 and/or GFR <60 mL/min/1.73m² (measured according to the MDRD calculation) will be excluded [39].

The use of loop diuretics is also not allowed if used within 24 hours prior to study drug administration.

Aseptic meningitis syndrome (AMS)

Aseptic meningitis syndrome has been reported to occur in association with IVIg treatment.

Discontinuation of IVIg treatment has resulted in remission of AMS within several days without sequelae. AMS may occur more frequently in association with high-dose of IVIGs.

Haemolytic anaemia

IVIg products can contain blood group antibodies which may act as haemolysins and induce in vivo coating of red blood cells with immunoglobulin, causing a positive direct antiglobulin reaction (Coombs' test) and, rarely, haemolysis. Haemolytic anaemia can develop subsequent to IVIg therapy due to enhanced red blood cells (RBC) sequestration.

Haptoglobin and LDH levels in patients will be assessed at every visit.

Interference with serological testing

After injection of immunoglobulin the transitory rise of various passively transferred antibodies in the patient's blood may result in misleading positive results in serological testing.

Passive transmission of antibodies to erythrocyte antigens, e.g. A, B, D may interfere with some serological tests for red cell antibodies for example the direct antiglobulin test (DAT), direct Coombs' test.

Interaction with other medicinal products

I10E may impair the efficacy of live attenuated virus vaccines for a period of up to 3 months. In the case of measles, this impairment may persist for up to 1 year.

Transmissible agents

Despite dedicated effective measures to prevent infections resulting from the use of plasma-derived products including selection of donors, screening of individual donations and plasma pools, as well as effective manufacturing steps for the inactivation/removal of viruses, the risk of transmitting infective agents cannot be totally excluded. This also applies to unknown or emerging viruses and other pathogens.

Patient serum reference samples will be drawn at the beginning and at the end of the study, and will be kept for long term storage.

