A scatter plot of the values at the EOS assessment as well as the minimum and maximum values of each patient during the treatment follow-up against the values at baseline will be prepared for each parameter. The first diagonal will be displayed by a dotted line.

4.7.3. 1.2. Course and infusion level analyses

Descriptive statistics of laboratory parameters at screening, before and 96h after the 1st IMP course, before the start of each subsequent course and at the EOS assessment will be provided for laboratory parameters as well as for the clinical assessment. The change from before first IMP course to 96h after the 1st IMP course as well as to before subsequent courses will be presented as well as the minimum and maximum values of each patient during the complete treatment follow-up. The complete treatment follow-up of maximum and minimum presentations includes all post-baseline assessments, along with any unscheduled assessment results which do not contribute to by visit descriptive summaries. Similarly, shift tables for the clinical assessment will be produced showing the change from before the first IMP course to 96h after the 1st IMP course as well as to before subsequent courses.

A graphical display of the evolution of each laboratory parameter by course will be presented with connected box-and-whisker plots. The number of observations at each visit will be displayed in the graph.

Detection of hemolysis will be evaluated at course level. The number and percentage of course with hemolysis will be displayed by subgroup and overall in accordance with the IVIg-associated hemolysis criteria published by Health Canada ([Health Canada 2009](#)), adapted to the study as follows:

- Drop in hemoglobin by at least 1 g/dL compared to baseline and
- At least one of the two criteria below are met
 - Positive direct Coombs test
 - At least 2 of the following criteria are met (in absence of negative direct Coombs test):
 - * Reticulocyte count increased by at least $50 \times 10^9/L$ compared to baseline
 - * LDH increased by at least 20% compared to baseline
 - * Haptoglobin value is lower than the lower limit of normal (LLN)
 - * Free bilirubin (or total bilirubin if the free bilirubin is not documented) increased compared to baseline and value is greater than the upper limit of normal (ULN)

In the following situations the courses will be excluded from the analysis:

Criterion for hemoglobin value cannot be evaluated/calculated

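### The SAP haemolysis count accepts a positive Coombs test plus a 1 g/dL haemoglobin fall, with no marker and no look at the screening result; flagged courses should be split by route and by screening status

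*Protocol*

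**What the plan says.** Protocol 9.2.1, under haemolytic anaemia, says that blood group antibodies in IVIg may "induce in vivo coating of red blood cells with immunoglobulin, causing a positive direct antiglobulin reaction", and that haemolysis follows only rarely. Under interference with serological testing it says that passively transferred red-cell antibody "may interfere with some serological tests for red cell antibodies for example the direct antiglobulin test (DAT), direct Coombs' test".

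The protocol had no haemolysis analysis, so the SAP added one (SAP 4.10.2), adapted from published Health Canada criteria. SAP 4.7.3.1.2 works by course and requires two things:

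- "Drop in hemoglobin by at least 1 g/dL compared to baseline and"
- either "Positive direct Coombs test", or at least two of four markers (reticulocytes, LDH, haptoglobin, bilirubin), the marker route being open only if there is no negative Coombs result.

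The planned output is the number and percentage of courses with haemolysis, by subgroup and overall. The dedicated listing for flagged patients covers haemoglobin, reticulocytes, LDH, haptoglobin and bilirubin. Baseline is the last value before the first course (SAP 4.3). The screening tests in Protocol 8.2.1 include "Reticulocytes, direct Coombs test" and haptoglobin.

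**The concern.** The protocol expects the product to turn some Coombs tests positive, mostly without haemolysis. The SAP treats the same result as enough to classify a course as haemolysis once haemoglobin has fallen by 1 g/dL. Within one list, haemoglobin, reticulocytes, LDH and bilirubin are judged as changes from baseline, while Coombs and haptoglobin are judged on their current value, although both have a screening result.

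Haemolytic anaemia is among the important potential risks named in Protocol 9.2.1. The planned table would put three kinds of course under one percentage: those with biochemical evidence of red-cell destruction, those with a positive Coombs test and nothing else, and those where the Coombs or haptoglobin finding predates treatment. A reader of the study report could take all of them as drug-induced haemolysis.

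**Working it through.** The plan states no figure to reproduce, so the check sets the criteria side by side and then enumerates the rule.

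**Step 1. Which elements use baseline, and when they are measured** (SAP 4.7.3.1.2 and 2.6; Protocol 8.2 and 8.3).

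| Element | Compared with baseline? | Measured |
|---|---|---|
| Haemoglobin | Yes | Screening, then Visit 3 to EOS |
| LDH | Yes | Screening, then Visit 3 to EOS |
| Bilirubin | Yes, and must exceed ULN | Screening, then Visit 3 to EOS |
| Reticulocytes | Yes | Screening and EOS; otherwise on suspicion |
| Haptoglobin | No | Screening, then Visit 3 to EOS |
| Coombs | No | Screening and EOS; otherwise on suspicion |

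**Step 2. Does anything else remove pre-existing findings?** The exclusion criteria (Protocol 5.2.2) mention neither a positive Coombs test nor low haptoglobin. The course exclusions in SAP 4.7.3.1.2 concern only data that cannot be evaluated.

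**Step 3. Run the rule as written, with haemoglobin down by at least 1 g/dL.**

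- Coombs positive and unchanged since screening, no marker met: flagged.
- Coombs missing, haptoglobin low and unchanged since screening, LDH up 20%: flagged.
- Coombs missing, low haptoglobin the only marker: not flagged.
- Coombs negative, low haptoglobin and LDH up 20%: not flagged.

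**Step 4. Count the patterns.** Three Coombs states and four yes/no markers give 3 × 2⁴ = 48.

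- Coombs positive: all 16 flagged.
- Coombs missing: C(4,2) + C(4,3) + C(4,4) = 6 + 4 + 1 = 11 flagged.
- Coombs negative: 0 flagged.
- Total: 16 + 11 = 27 of 48.

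Of the 16, C(4,0) + C(4,1) = 1 + 4 = 5 have fewer than two markers and are flagged only because of Coombs. Of the 11, C(3,1) = 3 have low haptoglobin as one of exactly two markers. These are counts of patterns, not frequencies.

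**Step 5. Where the Coombs-only route acts.** Under Protocol 8.3, Coombs is done between screening and EOS only when haemoglobin, haptoglobin, LDH or bilirubin raises suspicion. At EOS it is due in every patient. For a patient who completes treatment, EOS follows course 8, when the patient has had eight courses of IVIg.

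**Step 6. Can the mandatory haemoglobin fall be met without haemolysis?** This is an illustration only: the documents give no within-patient SD, so normal, independent measurements with an assumed SD are used. For a true mean fall δ, P(observed fall ≥ 1) = 1 − Φ[(1 − δ)/(SD√2)].

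| Assumed SD (g/dL) | δ = 0 | δ = 0.5 |
|---|---|---|
| 0.3 | 0.9% | 12% |
| 0.5 | 7.9% | 24% |
| 0.7 | 15.6% | 31% |

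The haemoglobin condition filters well or poorly depending on the assumption. These are not rates of falsely flagged courses, which also need a positive Coombs test or two markers.

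**The case against.** The strongest case for leaving the rule alone has five parts.

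- **It is a published rule, and sensitivity is a virtue in safety.** The SAP states that it adapts Health Canada criteria. That source is not available here, so whether it requires new onset cannot be checked. This stands, and is a reason to keep the rule as the overall count.
- **The Coombs-only scenario is narrow.** Outside EOS the test is done only on suspicion. This stands. A reader might infer that a patient who is Coombs-positive at screening is counted at every course; the schedule does not support that. It does not remove the problem at EOS.
- **Carry-over at screening may be uncommon.** Pretreated patients must be at least 3 months from their last Ig course, blood products within 3 months are excluded, and the protocol calls the passive antibody rise transitory. This stands for pre-existing positivity. It does not touch positivity that first appears on treatment.
- **Other analyses exist.** A reader might infer that this percentage is the only objective look at haemolysis. It is not: SAP 4.7.3.1.1 plans shift tables and changes from baseline, and SAP 4.7.2 includes a haemolytic-disorders SMQ. It is, however, the only analysis that classifies courses as haemolysis.
- **A new-since-screening condition is the wrong remedy.** Coombs positivity caused by the infused product is new since screening and would pass such a condition. For haptoglobin, the condition would cost sensitivity: a patient low at screening would need two of the other three markers, and with reticulocytes missing, both LDH and bilirubin. This stands, so the remedy should be a split display and not a redefinition.

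**Conclusion.** The point holds as a matter of reporting. The haemolysis count can include courses with no biochemical marker, on a test that the protocol says the product itself may turn positive. It ignores screening Coombs and haptoglobin results that are collected. The Coombs part is the stronger. The haptoglobin part is secondary, because low haptoglobin needs a second marker and the absence of a negative Coombs result.

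The size is unknown. A reader might want to state an inflation in percentage points or a false-positive probability. The documents give no rate of positive Coombs or low haptoglobin, at screening or on treatment. The denominator is also not the number of planned courses: read literally, the SAP drops courses with no Coombs result, one or two markers not evaluable, and fewer than two of the rest met. Reticulocytes follow the same limited schedule as Coombs, so many unflagged courses could drop out.

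The consequence is confined to a descriptive safety table. No hypothesis test depends on it, and the primary efficacy analysis is untouched. Because haemolysis is a named important risk and the data to separate the routes are already collected, the change should be made.

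**What to change.** In SAP 4.7.3.1.2, keep the adapted rule as the overall count and add three rows to the table:

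- (a) Coombs-positive with at least one of the four markers met;
- (b) Coombs-positive with no marker met;
- (c) markers only.

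Within each row, show separately the courses of patients whose Coombs test was already positive, or whose haptoglobin was already below LLN, at screening. Rows (a) and (b) should be fillable in most cases, because reticulocytes are scheduled or triggered together with Coombs.

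Add the Coombs result, screening and current, to the dedicated haemolysis listing. SAP 5.1 promises listings of all data, but without this addition a reader would have to rebuild each course's route from the general listings.

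The cost is a few table rows, one listing column pair, and some programming on data already collected. No further sampling is needed, and the count comparable with the adapted criteria is preserved.
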